10.2. Method of analysis

For the primary outcome, the absolute COMPASS-31 score will be compared between patients with/without infectious/cardiovascular complications (unpaired t-test). For secondary outcomes, individual components of the COMPASS-31 score, the presence/absence of individual components will be compared (Fisher exact test). Statistical analysis plans for both clinical and mechanistic studies will be published online before database closure.

11. Ethics

The Chief Investigator must ensure that the study is conducted in accordance with the guidelines of the International Conference on Harmonisation, GCP and UK legislation. All study documentation will be reviewed and approved by the research ethics committee prior to start of recruitment. Research Ethics Committee, Health Research Authority and Sponsor approvals will be in place before patient recruitment commences. The study will be sponsored by QMUL. Additionally, each participating site will ensure that the approval of the relevant trust Research & Development department and Ethics Committee is in place and a written confirmation is provided to the Sponsor.

12. Patient and Public Involvement (PPI)

The grant proposal for this study has been designed with the PPI members at The Patient, Carer & Public Involvement and Engagement (PCPIE) group at the Royal College of Anaesthetists. Furthermore, our PPI co-applicant have reviewed the protocol and will continue to advise us for the duration of the study including dissemination of the study results.

13. Data handling and record keeping

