5.6. Co-exposure of interest

The co-exposure of interest is:

- 1) Infectious complications within 30 days after surgery, a composite defined as one or more of the following infections of Clavien-Dindo grade II or greater. A full list of definitions is available in Appendix 1:
 - i. Superficial surgical site infection;
 - ii. Deep surgical site infection;
 - iii. Organ space surgical site infection;
 - iv. Pneumonia;
 - v. Urinary tract infection;
 - vi. Laboratory confirmed blood stream infection;
 - vii. Infection, source uncertain (antibiotics given on clinical suspicion).

2) Cardiovascular morbidity defined as one or more of Standardised Endpoints and Core Outcome Measures for Perioperative Medicine and Anaesthetic Care (StEP-COMPAC) cardiovascular complications: myocardial infarction, myocardial injury, cardiovascular death, non-fatal cardiac arrest, coronary revascularisation, major adverse cardiac events, pulmonary embolism, deep vein thrombosis, and atrial fibrillation AND/OR hypotension (mean arterial pressure <60mmHg) detected as part of routine clinical care requiring pressor infusion within 30 days after surgery.

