6.2. Exclusion criteria

- · Lack of capacity or refusal to provide written informed consent
- Inability to complete questionnaires
- American Society of Anesthesiologists (ASA) score of I

7. Study design

Multi-centre observational cohort study across surgical services in NHS hospitals.

8. End of study

The end of the study is defined as the point when the last patient has completed the 30-day follow-up.

9. Study procedures

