10.1. Sample size

296 patients are required to have a 90% chance of detecting, as significant at the 1% level, a mean difference in COMPASS-31 score of 5 (SD:8) between an estimated ~20% patients who develop postoperative infections, compared with patients who remain free of infection after surgery (STATA).

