14.5. Sample and data recording/reporting

Troponin-T data will be measured by the WHRI laboratory and shared by secure electronic communication after the last patient sample has been analysed.

15. Safety reporting

Due to the nature and design of this study, reporting of safety related events will not occur.

16. Monitoring and auditing

The Sponsor or delegate retains the right to audit any study, study site or central facility. In addition, any part of the study may be audited by the funders where applicable. In participating hospitals, local study documents may be selected for audit on a local basis. However, the Pero-COMPASS 31 study team will not routinely monitor data collection in individual hospitals or conduct source data verification.

17. Study committees

The Peri-COMPASS 31 study will be managed by the Critical Care and Perioperative Medicine Research Group (CCPMG) based at Queen Mary University of London. The day-to-day conduct of the study trial will be led by the trial management group, under the management of the Chief Investigator(s) or nominated deputy.

18. Finance and funding

The study is part of a PhD project and is funded by King Saud bin Abdulaziz University for Health Sciences and Queen Mary University of London. The funders will play no role in study design, conduct, data collection, data analysis, reporting or interpretation of the results.

19. Insurance and indemnity

The insurance that Queen Mary has in place provides cover for the design and management of the study as well as "No Fault Compensation" for participants, which provides an indemnity to participants for negligent and non-negligent harm.

20. Dissemination of research findings

Data arising from this research will be made available to the scientific community in a timely and responsible manner. A detailed scientific report will be submitted to a widely accessible scientific journal on behalf of the Peri-COMPASS 31 study group. At least

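### The primary t-test pools hospitals, so its 1% level is not assured if recorded infection rates and COMPASS-31 scores both differ by hospital; a hospital term is a cheap, minor improvement

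*Protocol*

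**What the plan says.** Protocol section 7 describes the design as "Multi-centre observational cohort study across surgical services in NHS hospitals". The number of hospitals is not given. Section 10.2 names one primary test: "the absolute COMPASS-31 score will be compared between patients with/without infectious/cardiovascular complications (unpaired t-test". Neither 10.1 nor 10.2 mentions hospital, by stratification, model term or allowance for clustering.

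Section 10.1 sets a total of 296 for 90% power, and the effect is to be detected "as significant at the 1% level". The target effect in that section is "a mean difference in COMPASS-31 score of 5 (SD:8". The group split it assumes is "an estimated ~20% patients who develop postoperative infections".

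Infection is a composite in section 5.6, restricted to Clavien-Dindo grade II or above, with definitions referred to an appendix. One component is "Infection, source uncertain (antibiotics given on clinical suspicion". The medical notes are the source (13.2), and each site's own team enters the data (13.1). The coordinating team reviews entries for gaps and internal agreement (13.1), but section 16 says the study team "will not routinely monitor data collection in individual hospitals or conduct source data verification". Under section 9.3 the questionnaire may be completed in person or remotely.

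**The concern.** An unpaired t-test treats the 296 patients as independent draws from two populations. In a multi-centre cohort the observed difference in means has two parts: the difference between infected and uninfected patients in the same hospital, and a part that arises because hospitals supplying more recorded infections may also have higher or lower scores. The second part does not bear on the protocol's question, which is about individuals.

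The document gives a concrete route by which recorded infection rates can differ: local prescribing on suspicion, local notes, local data entry and no routine source verification. Eligibility covers any elective major noncardiac surgery in patients aged 50 or over with ASA above I. Case-mix, and with it both infection risk and symptom score, can therefore differ between sites.

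Two things are at stake. If the hospital effects on infection and on score are correlated, the pooled difference is biased. If they are uncorrelated, a small number of hospitals can still align by chance, and the t-test's standard error does not cover that. Either way the stated 1% level may not hold.

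**Working it through.** **Inputs from the protocol.** N = 296, difference 5, SD 8, 20% infected, 1% level, 90% power (10.1). Sidedness is not stated; two-sided is taken.

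**Assumed, because the protocol gives none of them.** The number of hospitals, the hospital share of score variance (ICC), the between-hospital SD of the log-odds of infection, and the correlation between the two hospital effects.

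**1. The plan's own figure.** With four uninfected patients per infected patient:

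n(infected) = (2.576 + 1.282)² × 8² × (1 + 1/4) / 5² = 14.88 × 3.2 = 47.6, so 48 + 192 = 240 in total, or 49 + 196 = 245 with the t distribution.

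The stated 296 is not reproduced. At 296 the stated inputs give 95.5 to 95.8% power. That is a separate matter and errs on the large side. The checks below use 296.

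**2. Scale.** With 59 infected and 237 uninfected, SE = 8 × √(1/59 + 1/237) = 1.16 points. An observed difference of about 2.59 × 1.16 = 3.0 points is needed for p < 0.01.

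**3. Simulation under no true association.** For hospital j with standard normal effects u and v, correlated at ρ:

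- infection: logit p(j) = ln(0.20/0.80) + s·u(j)
- score: 8 × [√ICC · v(j) + √(1 − ICC) · patient error]

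There were 20,000 studies per scenario, with hospitals of equal size. The Monte Carlo standard error at 1% is √(0.01 × 0.99 / 20,000) = 0.07 percentage points. The table gives the percentage of studies rejecting at a nominal 1%; rates are 95% ranges of hospital infection rates.

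| ICC | s | Rates | ρ | Pooled, 5 / 10 hospitals | Hospital fixed effect, 5 / 10 |
|---|---|---|---|---|---|
| 0.05 | 0 | 20% in all | – | 1.0 / 0.9 | 1.0 / 0.9 |
| 0 | 0.5 | 9–40% | – | 1.0 / 1.0 | 1.0 / 1.0 |
| 0.02 | 0.3 | 12–31% | 0 | 1.1 / 1.2 | 1.0 / 1.1 |
| 0.02 | 0.3 | 12–31% | 0.5 | 1.1 / 1.0 | 1.1 / 0.9 |
| 0.05 | 0.5 | 9–40% | 0 | 1.5 / 1.4 | 1.0 / 1.1 |
| 0.05 | 0.5 | 9–40% | 0.5 | 1.9 / 1.8 | 1.1 / 1.1 |
| 0.10 | 0.8 | 5–55% | 0 | 3.3 / 2.1 | 1.2 / 0.9 |
| 0.10 | 0.8 | 5–55% | 0.5 | 6.3 / 5.5 | 1.0 / 1.0 |

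The first two rows show that the pooled test keeps its level when only scores or only infection rates differ.

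Further runs with 5 to 10 hospitals:

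- ICC 0.05, s = 0.4, ρ = 0.5: 1.5 to 1.8%, with a spurious difference of about 0.3 points.
- ICC 0.10, s = 0.7, ρ = 0.5 to 0.8: about 5 to 9%. Here ln(0.25) ± 1.96 × 0.7 is −2.76 to −0.01, so hospital infection rates run from about 6% to 50%.

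Over 3 to 20 hospitals the fixed-effect test stayed at 0.8 to 1.2% in every scenario.

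**4. Power of the alternative.** For a true difference of 5 with ICC 0.05, s = 0.5 and unrelated hospital effects, the fixed-effect model gave 95.7% (5 hospitals) and 95.1% (10 hospitals). The pooled t-test gave 95.0% and 94.9%.

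**The case against.** The strongest reply is about scope. Section 10.2 gives the test in one sentence and promises analysis plans before database closure; handling of centre is often settled there, and nothing in 10.2 forbids it. This stands in part: the unseen plan may already include hospital. But the protocol names a specific pooled test, so it has fixed a method, and 10.2 would have to be brought into line with any such plan.

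The second reply is that the size is small, and this largely stands. Under mild to moderate assumptions the inflation is negligible to about twofold. A spurious 0.3 to 0.4 points is small against a target of 5 and the roughly 3.0 points needed for significance. The grade threshold, the written definitions and the central review should also limit differences between hospitals, although that review would not detect differing local thresholds for suspecting infection.

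The third reply is that a hospital term does not repair confounding by case-mix among patients of the same hospital. This stands in full. With an assumed patient-level factor correlated 0.25 with score and with log-odds 0.5 for infection, the pooled and the hospital-adjusted tests both rejected about 3.6%, each with about 0.95 points of bias.

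A reader might infer three stronger things. One is that infection rates and scores are bound to differ by hospital: the documents show only that they can. Another is that sites choose how COMPASS-31 is collected: section 9.3 does not say so, and for electronic completion it refers to the patient's preference. The third is that the usual cluster design effect applies in full: it does not, because infection status varies between patients within a hospital.

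**Conclusion.** The point holds in a limited form. The protocol fixes a pooled unpaired t-test for a multi-centre study. If recorded infection rates and COMPASS-31 scores both differ by hospital, the stated 1% level is not assured; if only one differs, the level is unaffected.

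The size depends wholly on assumed figures (5 to 10 hospitals, N = 296):

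- about 1.0 to 1.4% for mild heterogeneity or unrelated hospital effects (ICC 0.02 to 0.05, logit SD 0.3 to 0.4);
- about 1.5 to 2% for ICC 0.05, logit SD 0.4 to 0.5 and correlation 0.5;
- about 5 to 9% only when heterogeneity is strong and the hospital effects are correlated at 0.5 to 0.8.

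The documents support no particular value of the correlation, so the last range shows what could happen and is not a forecast. Severity is minor: a cheap improvement, not a demonstrated failure of the primary analysis.

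**What to change.** In section 10.2, replace the pooled t-test with a linear model of total COMPASS-31 score on infection status, with hospital as a fixed effect. State a rule for grouping hospitals with very few patients. Keep the unadjusted difference in means as description, and make the analysis plan agree before it is published.

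The cost is a wording change in the protocol and the plan, with no new data, because each site enters its own patients. The model uses one degree of freedom per hospital, with essentially no loss of power (about 95 to 96% either way for a 5-point difference). Adjustment for patient-level confounders is a separate decision that this change does not settle.

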4.1. Background

Experimental and clinical association studies show that autonomic dysfunction causes, augments, systemic inflammation,⁽¹⁾ infections,⁽²⁾ myocardial injury, (3) gastrointestinal complications⁽²⁾ and lung injury.⁽⁴⁾ As perioperative morbidity typically involves several organs, generalised loss of autonomic function is a plausible unifying pathological driver underlying infectious complications after major surgery. However, screening/ identifying autonomic dysfunction in patients before surgery is rather more challenging and has not been systematically explored at scale. The Composite Autonomic Symptom Score-31 (COMPASS-31) score may provide in-depth assessment of autonomic abnormalities in different organs before surgery. (5) This scale includes 31 questions pertaining to mainly six domains of sympathovagal imbalance dysfunction, such as gastrointestinal vasomotor imbalance, secretomotor disturbances, pupillomotor abnormalities, orthostatic intolerance, and urinary dysfunction. The total scoring if added, usually ranges between zero and 100, with a maximum score of 40 for orthostatic intolerance followed by 25 for gastrointestinal dysfunction, 15 for glandular abnormalities, and 10 for urinary ailments with five each for vasomotor and pupillomotor problems, respectively. The scale has an outstanding internal validity of 0.9. However, preoperative COMPASS-31 has not been examined or related to perioperative outcomes including infection and myocardial injury, common complications that prevents recovery and rehabilitation. Moreover, preoperative COMPASS-31 has not been validated against deliverable, objective measures of autonomic dysfunction including heart rate variability. (6)

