4.2. Rationale

To provide a mechanistic understanding of why, and which elements of, autonomic dysfunction predisposes individuals to infectious and/or cardiovascular complications following major noncardiac surgery.

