5.5. Secondary outcome measures

Individual components of the COMPASS-31 questionnaire: orthostatic intolerance, vasomotor, secretomotor, gastrointestinal, bladder, pupillomotor abnormalities.

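### Section 10.2 reduces the six graded COMPASS-31 domain scores to present/absent with Fisher's exact test, which discards severity and can cost much of the power to show which domains matter

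*Protocol*

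**What the plan says.** Section 4.1 of the Protocol describes COMPASS-31 as a weighted scale running from 0 to 100, "with a maximum score of 40 for orthostatic intolerance followed by 25 for gastrointestinal dysfunction, 15 for glandular abnormalities, and 10 for urinary ailments", and "with five each for vasomotor and pupillomotor problems". The six maxima (40, 25, 15, 10, 5 and 5) add to 100.

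Section 5.5 makes these domains the secondary outcome measures: "Individual components of the COMPASS-31 questionnaire: orthostatic intolerance, vasomotor, secretomotor, gastrointestinal, bladder, pupillomotor abnormalities".

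Section 10.2 treats the total and its parts differently. The total stays on its scale: "the absolute COMPASS-31 score will be compared between patients with/without infectious/cardiovascular complications (unpaired t-test"). For the parts, "the presence/absence of individual components will be compared (Fisher exact test"). No reason is given for the difference.

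Section 4.2 states the purpose that a domain analysis serves: to understand why, and "which elements of, autonomic dysfunction predisposes individuals to infectious and/or cardiovascular complications".

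**The concern.** A domain score records how much symptom burden a patient has. Once it is coded as present or absent, a patient with a trivial score and one near the maximum count the same, if presence means any symptom. The orthostatic domain runs up to 40 points and the gastrointestinal domain up to 25, so there is a good deal of gradation to lose.

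The domain comparison is the only analysis in section 10.2 that can say which elements of autonomic dysfunction go with complications. If a symptom is common, almost every patient is coded present in both groups and the test has little left to compare, even where severity differs. A null result for such a domain could then reflect the coding rather than the biology.

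This is not a detail left to the statistical analysis plan. The protocol itself fixes both the binary coding and the test. A later plan can add a cut-off, but a cut-off does not bring back the severity that binary coding drops.

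**Working it through.** **The plan's own figure.** Section 10.1 says that "296 patients are required to have a 90% chance of detecting" a difference of 5 (SD 8) at the 1% level, with about 20% infected. It concerns the total score only; no figure is given for the domains. With a 1:4 split, the infected group needs (z₀.₉₉₅ + z₀.₉₀)² × (SD/Δ)² × (1 + 1/4) = (2.576 + 1.282)² × (8/5)² × 1.25 = 14.88 × 2.56 × 1.25 = 47.6, so 48. The uninfected group needs 191, total 239 (242 with the noncentral t distribution). The stated 296 is larger and gives about 95.5% power for the total score. The difference is on the safe side and does not bear on this point. What is used from here is the group split: 20% of 296 is 59 infected, leaving 237.

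**Inputs for the domain comparison**
- From the Protocol: 59 vs 237 patients and the 1% level (section 10.1; two-sided assumed); Fisher's exact test on presence (section 10.2).
- Assumed, because the Protocol gives no domain prevalence, SD or effect: a latent normal domain score shifted by 0.5 SD in infected patients, and a range of prevalences p₀ in the uninfected.

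**Step 1: information kept by a binary split.** For a normal score split so that a proportion p is present, with c = Φ⁻¹(1 − p), the efficiency relative to the full, unfloored score is φ(c)² / [p(1 − p)].

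| p | Efficiency | Information lost |
|---|---|---|
| 50% | 0.64 | 36% |
| 70% | 0.58 | 42% |
| 80% | 0.49 | 51% |
| 90% | 0.34 | 66% |

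The formula is symmetric, so 20% behaves as 80%.

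**Step 2: power with scores floored at zero.** Step 1 flatters the full score where many patients score zero, because tied zeros carry no severity. So all latent values below the threshold are set to zero, and the rank-sum test is applied to that heaped score. Presence in the infected is p₁ = Φ(0.5 + Φ⁻¹(p₀)); for example, p₀ = 80% gives p₁ = Φ(0.5 + 0.842) = 91%. Simulated power, two-sided 1%:

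| Present, uninfected | Present, infected | Fisher on presence | Rank-sum on score |
|---|---|---|---|
| 10% | 22% | 39% | 47% |
| 20% | 37% | 49% | 58% |
| 50% | 69% | 52% | 73% |
| 70% | 85% | 35% | 75% |
| 80% | 91% | 24% | 77% |
| 90% | 96% | 8% | 76% |

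The figures carry simulation error of about two percentage points. The gap is 8 to 9 points when the domain is uncommon, 21 at 50% presence, and 53 to 68 at 80 to 90%.

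**Step 3: the case that favours Fisher.** Let the groups differ only in how many patients have the symptom, with equal severity among those affected.

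| Present, infected vs uninfected | Fisher | Rank-sum |
|---|---|---|
| 30% vs 10% | 85% | 88% |
| 45% vs 20% | 89% | 90% |
| 55% vs 30% | 82% | 81% |
| 75% vs 50% | 83% | 70% |

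Here the tests are about equal in the first three cases, and Fisher is clearly better in the last.

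**The case against.** The strongest reply is that the size of the loss is not known. The Protocol gives no domain prevalence, and nothing in it shows that any domain is present in most patients. If a domain is uncommon, Fisher gives up only 8 to 9 points of power in step 2. If the signal lies in occurrence rather than severity, step 3 shows Fisher doing as well or better. That stands, and it is why the results are given as a range.

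It is also fair that these are secondary outcomes, that the primary comparison keeps the total on its scale, and that the objectives in sections 5.1 and 5.2 speak of COMPASS-31 scores without naming a domain comparison. The questionnaire is collected in full, so nothing is irrecoverable. This limits the weight of the point but does not remove it, because section 4.2 asks which elements matter and nothing else in section 10.2 answers that.

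Three stronger readings are tempting, and the documents support none of them.
- That most of the information is lost. Under the normal model the loss passes half only at about 80% presence or more, or 20% or less, and the Protocol does not say where any domain lies.
- That a common domain cannot show an association. Power is reduced, to 24% at 80% presence and 8% at 90%, but it is not zero.
- That the domains would end up ranked by how common their symptoms are. Power does depend on prevalence, but no ranking was examined.

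The cut-off for presence and any multiplicity rule across domains can properly be left to the analysis plan, and are not part of this point.

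**Conclusion.** The point holds in a limited form. The Protocol scores the domains on graded scales, keeps the total as a number, and then fixes a binary test for the parts without giving a reason. Severity is discarded, and the power lost can be large. In the floored model with a 0.5 SD latent shift, the cost runs from 8 to 9 points when 10 to 20% of uninfected patients have the domain present to 68 points at 90%. The direction is not universal: where only occurrence differs, the two tests are about level or Fisher is ahead (83% vs 70% at 75% vs 50% presence).

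The result rests on an assumed effect, an assumed distribution and an assumed range of prevalences. That the coding is binary, and that this drops severity, rests on the text alone. The change is worth making because the better analysis is nearly free. It does not affect the primary comparison.

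**What to change.** In section 10.2, replace the Fisher comparison as the secondary analysis by a comparison of each domain score on its own scale: a Wilcoxon rank-sum test, or logistic regression per SD of the domain score. Keep the percentage of patients with each domain present, at a pre-specified cut-off, as a descriptive supplement. Make the change before database closure, which section 10.2 already sets as the deadline for publishing the analysis plans.

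The cost is wording only. The domain scores are already computed to obtain the total, and no further data or patients are needed. The one downside is some loss of power if the signal lies purely in the occurrence of a common symptom; the descriptive percentages would still show that pattern.
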